5.2.1. Screening Visit (14 \pm 3 days prior to Day 0)

The subject will be informed about the general aspects of the study and will sign the screening informed consent form. The subject number will be allocated once the subject will be created in the eCRF. Only when consent has been given may further study procedures be carried out. During the screening phase, the following assessments will be performed:

- Signed informed consent form;
- · Demographic data: date of birth and gender;
- · Body weight and height;
- Medical history;
- Physical examination and vital signs;
- Hematology and Biochemistry including pregnancy test for all women of childbearing potential;
- 12 leads ECG;
- · Sigmoidoscopy with rectal/sigmoidal biospies;
- Rectal Microbiota sampling (Swab);
- Total Mayo Score;
- Clostridium difficile (stool antigen and toxin), CMV, TB;
- Give the "Subject Diary" and instruct the subject how to use it.

- Record all medications received within 3 months prior to baseline and note if the medication is continuing;
- Inclusion/exclusion criteria will be verified globally.

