If changes in severity for the same TEAE have been reported separately but with the same adverse event (AE) number, they will be collapsed to a single AE with maximum severity for the summary tables, but listed as reported.

Classifications of medical history, concomitant medication and adverse events will be sorted alphabetically within the summary tables.

If any laboratory assessments are repeated at the same visit, the result from the repeat assessment will be used in summaries. Both values will be listed.

Data collected on the eCRF will be presented within data listings. The data listings will be sorted by treatment group, country, centre number, patient number and visit/week/day. Treatment group will be as allocated (randomised). If any patients receive the wrong treatment this will be flagged in all listings. Visits outside the visit windows will be identified within the listings.

The date format for all output presentations will be 'ddMMMyyyy'.

All statistical analysis will be performed using SAS 9.3 or higher.

P-values will be rounded to four decimal places. P-values less than 0.0001 will be reported as <0.0001 in tables.

If any of the assumptions underlying the formal statistical methods proposed are violated during the analysis of the final data, alternative statistical methods will be used and any changes documented in the statistical methods section of the CSR, including the rationale for use.

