11.2.3 Disease History and Characteristics

Time since UC diagnosis (years) will be summarised for the FAS (*Table 14.1.6*) and is derived as (date of informed consent - date of UC diagnosis) / 365.25. The stratification factors, concomitant treatment with corticosteroids (yes, no) and previous biologics exposure (yes, no), will be summarised within the same table.

The faecal calprotectin levels recorded at baseline will be summarised descriptively (*Table 14.1.7*). TMS, PMS and MH and PH component summary measures from the SF-36 questionnaire collected at baseline will be also be summarised descriptively within the same table. Note that the TMS encompasses the PMS (number of stools, blood in stools and severity assessment) and the endoscopy sub-score. The baseline endoscopy is performed at screening while the PMS is assessed both during the screening and the Day

0 visits. Therefore the baseline TMS value will be derived by adding the endoscopy sub-score performed at screening with the PMS done at Day 0.

The number and proportion of patients with concomitant use of medications for UC will be summarised by all categories, some of which are corticosteroid only, immunosuppressants only, combination treatment or no treatment (*Table 14.1.8*). The number and proportion of patients with prior biological failure (categorised as TNF or others / vedolizumab) will also be presented within the same table.

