11.6 PRIOR AND CONCOMITANT MEDICATION

All medications taken by patients on entry to the study or during the study will be recorded in the eCRF. Medications will be classified using the version of the World Health Organisation Drug Dictionary (WHODD) coding dictionary defined in the DMP. The Anatomical Therapeutic Chemical (ATC) Classification and WHO-DRUG PT will be used to list and summarise the data.

Prior medications are defined as all medications that started and stopped before date of first dose. Only medications where the stop date is prior to date of first dose will be considered prior. If the stop date is unknown or incomplete and the medications cannot definitely be considered as stopped prior to date of first dose then the medications will be considered as concomitant medications.

Concomitant medications are defined as all medications that started on or after date of first dose.

The number (%) of patients reporting the use of any prior medications and the number (%) of patients taking each drug by ATC classification (1st, 2nd and 4th levels) and PT will be summarised using the FAS (Table 14.3.6.1).

This table will be repeated for concomitant medications (Table 14.3.6.2).

[figure not shown]

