Diastolic BP (mmHg) Heart Rate (bpm)				
Body temperature (°C) Weight (kg)				
ource: Listing 16.x.x ath\Filename				Page x/y

Version date: 23 August 2018

Page 59 of 93

ABX464-101

Table 14.3.4.1 12-Lead Electrocardiogram (Safety Set)

ddMMMyyyy

		ABX-464	Placebo	Total
		(N=xx)	(N=xx)	(N=xx)
Baseline	N	xx	xx	xx
	Normal	xx (xx.x%)	xx (xx.x%)	xx (xx.x%)
	Abnormal NCS	xx (xx.x%)	xx (xx.x%)	xx (xx.x%)
	Abnormal CS	xx (xx.x%)	xx (xx.x%)	xx (xx.x%)

Etc

Source: Listing 16.x.x

Path\Filename

Page x/y

Version date: 23 August 2018

Page 60 of 93

GROUP

ABX464-101

Table 14.3.5 Study Drug Exposure (Full Analysis Set)

ddMMMyyyy

		ABX-464 (N=xx)	Placebo (N=xx)	Total (N=xx)
Number of dose intakes	N	xx	××	xx
	Mean	xx.xx	xx.xx	xx.xx
	SD	xx.xx	xx.xx	xx.xx
	Median	xx.xx	xx.xx	xx.xx
	Minimum	xx.x	xx.x	xx.x
	Maximum	xx.x	xx.x	xx.x
Study drug exposure (days)	N	xx	xx	xx
orday and exposure (days)	Mean Etc	xx.xx	xx.xx	xx.xx

Study drug exposure (days) is calculated as (date of last dose) - (date of first dose) + 1

Source: Listing 16.x.x

Path\Filename Page x/y

Version date: 23 August 2018

Page 61 of 93

Table 14.3.6.1 Prior Medications (Full Analysis Set)

ddMMMyyyy

	ABX - 464	Placebo	Total
www.	(N=xx)	(N=xx)	(N=xx)
Any prior medication	xx (xx.x%)	xx (xx.x%)	xx (xx.x%)
X, xxxxxxxxxxxx	xx (xx.x%)	xx (xx.x%)	xx (xx.x%)
XON, xxxxxxxxxxxx	xx (xx.x%)	xx (xx.x%)	xx (xx.x%)
XONXX, xxxxxxxxxxx	xx (xx.x%)	xx (xx.x%)	xx (xx.x%)
xxxxxxxxxxx	xx (xx.x%)	xx (xx.x%)	xx (xx.x%)
Etc	xx (xx.x%)	xx (xx.x%)	xx (xx.x%)
XONXX, xxxxxxxxxx	xx (xx.x%)	xx (xx.x%)	xx (xx.x%)
xxxxxxxxxxx	xx (xx.x%)	xx (xx.x%)	xx (xx.x%)
Etc	xx (xx.x%)	xx (xx.x%)	xx (xx.x%)
XON, xxxxxxxxxxxx	xx (xx.x%)	xx (xx.x%)	xx (xx.x%)
XONXX, xxxxxxxxxxx	xx (xx.x%)	xx (xx.x%)	xx (xx.x%)
xxxxxxxxxx	xx (xx.x%)	xx (xx.x%)	xx (xx.x%)
Etc	xx (xx.x%)	xx (xx.x%)	xx (xx.x%)

Etc

Version date: 23 August 2018

Page 62 of 93

¹ Medication that stopped prior to date of first dose

WHO-DDE version <XX.X>

The denominator for each percentage is the number of patients in the full analysis set within the column

Source: Listing 16.x.x Path\Filename

Page x/y

This layout also applies to: Table 14.3.6.2 Concomitant Medications (Full Analysis Set)

Version date: 23 August 2018

Page 63 of 93

ABX464-101

Listing 16.2.1 Discontinued Patients and Reason for Withdrawal

ddMMMyyyy

Treatment	Centre/ Patient number	First dose date	Last dose date	Date of withdrawal	Main reason for withdrawal

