		**************************************	**************************************	*************	XXXXXXXXXXXX XX.X XXXXXXX XX.X XXXXXXXX	**************************************	**************************************	XXXXXXXXXXXXX XXXXXXXXXXXXXX XXXXXXXXXXXXXX XXXXXXXXXXXXXXXXXXXXXXXXXXXXXXXXXXXX

Etc

Page x/y

Version date: 23 August 2018

Page 87 of 93

Path\Filename

This layout also applies to: Listing 16.4.11 Concomitant Medications (Programming note: can have stop date as 'ongoing')

Version date: 23 August 2018

ABX464-101

Listing 16.4.12 Procedures/ Non-Drug Therapies

ddMMMyyyy

Centre/ Patient	Procedure /Therapy	Start date	Ongoing / End date	Given for pre- existing condition?	Given for adverse event?		
number				(Related medical history number)	(Related adverse event number)		
xxx-xxxx	*****	ddMMMyyyy	Yes / No (ddMMMyyyy)	Yes (xxx) / No	Yes (xxx) / No		
	xxxxxxxxxxxx	ddMMMyyyy	Yes / No (ddMMMyyyy)	Yes (xxx) / No	Yes (xxx) / No		
	*****	ddMMMyyyy	Yes / No (ddMMMyyyy)	Yes (xxx) / No	Yes (xxx) / No		
	Patient number	Patient number xxx-xxxx xxxxxxxxxxxxxxxxxxxxxxxxxxxx	Patient number xxx-xxxx xxxxxxxxxxxx ddMMMyyyy xxxxxxxxxxxxxxx ddMMMyyyy	Patient number date xxx-xxx xxxxxxxxxxxxxx ddMMMyyyy Yes / No (ddMMMyyyy) xxxxxxxxxxxxxxxx ddMMMyyyy Yes / No (ddMMyyyy) xxxxxxxxxxxxxxxxx ddMMMyyyy Yes / No	Patient number date existing condition? (Related medical history number) XXX-XXXX XXXXXXXXXXXX ddMMMyyyy Yes / No Yes (XXX) / No (ddMMMyyyy) XXXXXXXXXXXXXXXX ddMMMyyyy Yes / No Yes (XXX) / No Yes (XXX) / No		

Path\Filename

Version date: 23 August 2018

Page 89 of 93

ABX464-101

[figure not shown]
Listing 16.4.13 Pregnancy Test

ddMMMyyyy

Treatment	Centre/ Patient number	Visit	Test done	Reason not done	Date of test	Result
xxxxx	xxx-xxxx	Screening	Yes/No/Not applicable	*******	ddMMMyyyy	Positive/Negative
		xx	Yes/No/Not applicable	xxxxxxxxxxx	ddMMMyyyy	Positive/Negative
		xx*	Yes/No/Not applicable	*******	ddMMMyyyy	Positive/Negative
		xx	Yes/No/Not applicable	*********	ddMMMyyyy	Positive/Negative
		Etc				
Etc						
*Outside the	visit window					Page x/y
Path\Filename	•					

Version date: 23 August 2018

Page 90 of 93

Statistical Analysis Plan

ABX464-101

Listing 16.4.14 Laboratory and Other Assessment Samples Collection

ddMMMyyyy

Parameter xxxxxx	Treatment	Centre/ Patient number	Visit	Sample taken ng Yes/No	Reason not done	Date of test ddMMMyyyy	Result	Interpretation			
	xxxxx		Screening					Normal/ Abnormal CS/ Abnormal			

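### SAP 11.6 leaves a medication started before first dose and stopped on study in neither the prior nor the concomitant class, so Table 14.3.6.2 and Listing 16.4.11 would under-report on-study use

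*SAP*

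**What the plan says.** SAP 11.6 sorts medication records by their dates relative to first dose.

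- Prior: "Prior medications are defined as all medications that started and stopped before date of first dose". The next sentence restricts the class to records whose stop date precedes first dose.
- Bridging rule, which sends a record to concomitant: "If the stop date is unknown or incomplete and the medications cannot definitely be considered as stopped prior to date of first dose".
- Concomitant: "Concomitant medications are defined as all medications that started on or after date of first dose".

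Tables 14.3.6.1 (prior) and 14.3.6.2 (concomitant) then count FAS patients by ATC level and preferred term. Listings 16.4.10 and 16.4.11 use the same split. The SAP names no third medication table by drug and no third medication listing.

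On background treatment, Protocol 4.2.1 requires oral steroids to be stable for at least two weeks before screening, and oral 5-ASA and immunosuppressants for four weeks. Protocol 3.1.1 describes a steroid taper from Week 4, in 5 mg weekly steps over four weeks, ending in discontinuation. Sections 3.1.1 and 3.1.2 both leave the taper to the investigator. Protocol 6.9.1 places these drugs under allowed concomitant treatment, and SAP 11.2.3 uses the same word: "The stratification factors, concomitant treatment with corticosteroids (yes, no) and previous biologics exposure (yes, no), will be summarised within the same table".

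**The concern.** The two definitions do not meet. Prior needs an early start and an early stop; concomitant needs a late start. A record with an early start and a late, fully dated stop satisfies neither, and the bridging rule does not reach it because its stop date is known.

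A background steroid withdrawn during treatment is exactly such a record, and the protocol and the SAP elsewhere both call it concomitant. A table meant to show what subjects took alongside study drug could omit it. A reader of the study report who compares background therapy between the arms would then see too little of it.

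**Working it through.** The plan gives no figure on this point, so there is nothing to reproduce. The check applies the rules to every feasible date pattern, then asks whether the protocol leads subjects into the gap.

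**Step 1. Classify the patterns.** Inputs are the three rules in SAP 11.6, with Day 0 as first dose.

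| Start | Stop | SAP 11.6 as written | With the fix |
|---|---|---|---|
| before Day 0 | before Day 0 | prior | prior |
| before Day 0 | Day 0 or later, complete date | neither | concomitant |
| before Day 0 | ongoing | depends on reading | concomitant |
| before Day 0 | unknown or incomplete, not shown to precede Day 0 | concomitant (bridging rule) | concomitant |
| Day 0 or later | Day 0 or later | concomitant | concomitant |
| Day 0 or later | ongoing | concomitant | concomitant |
| Day 0 or later | unknown or incomplete | concomitant | concomitant |

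As written: 1 prior + 4 concomitant + 1 neither + 1 reading-dependent = 7. With the fix: 1 prior + 6 concomitant = 7, none unassigned.

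**Step 2. Can background drugs start on study?** Inputs are the screening visit at Day -14 ± 3 and the stability periods in Protocol 4.2.1.

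- Latest screening: -14 + 3 = Day -11.
- Latest start of an oral steroid: -11 - 14 = Day -25.
- Latest start of oral 5-ASA or an immunosuppressant: -11 - 28 = Day -39.

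All precede Day 0, so none of these drugs qualifies as concomitant through its original start date.

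**Step 3. When does a taper to zero end?** Inputs are 5 mg per week from Week 4 (Protocol 3.1.1) and the 20 mg/day prednisone-equivalent cap (Protocol 4.2.1). Four steps of 5 mg remove 20 mg, which matches the cap. For starting dose D, the number of cuts is k = D/5. The text does not say whether the first cut falls at the start or the end of the first taper week, so both are shown.

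| D (mg/day) | k | First cut on Day 28: 28 + 7(k - 1) | First cut at end of that week: 28 + 7k |
|---|---|---|---|
| 5 | 1 | Day 28 | Day 35 |
| 10 | 2 | Day 35 | Day 42 |
| 15 | 3 | Day 42 | Day 49 |
| 20 | 4 | Day 49 | Day 56 |

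A completed taper ends at about Day 28 to 56: after first dose and normally with a recordable date. That is the second row of the table in Step 1.

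**Step 4. Which outputs move?** The prior class holds one pattern before the fix and the same one after it. Table 14.3.6.1 and Listing 16.4.10 therefore do not change. Only Table 14.3.6.2 and Listing 16.4.11 can gain records.

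**Step 5. Dependence on recording.** The documents do not show how dose changes are entered. If a whole course is one eCRF line (assumption), each completed taper falls in the gap. If each dose step is its own line (also an assumption), a taper from 10, 15 or 20 mg creates a later line that starts on study and is counted. Only a subject who stops in one step is then missed.

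**The case against.** The best defence is that SAP 11.6, read as a whole, is inclusive. Its opening covers medication taken on entry or during the study. If doubt about the stop date is enough to make a drug concomitant, a proven on-study stop should be too. The Table 14.3.6.1 footnote defines prior by stop date alone: "Medication that stopped prior to date of first dose". SAP 10.1 adds that "Data collected on the eCRF will be presented within data listings", SAP 12 requires independent quality control, and SAP 15 lets programmers adjust layouts.

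The intent probably is inclusive, and this is a drafting fault. But the sentence defining concomitant is explicit, and none of these places replaces it. The footnote concerns prior only. The general listing rule names no listing for an unclassified record. Quality control and layout freedom do not supply a classification rule.

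A reader might also infer several stronger things that the documents do not support.

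- That ongoing background drugs are certainly lost. Sites are told: "Record all medications received within 3 months prior to baseline and note if the medication is continuing", which suggests that continuing is a recorded status. Yet an ongoing drug has no stop date and fits the bridging rule naturally, and the shell allows the entry: "Listing 16.4.11 Concomitant Medications (Programming note: can have stop date as 'ongoing". This remains ambiguous.
- That the prior medication outputs are also wrong. Step 4 shows that they are not.
- That every steroid user will be missed. The taper is discretionary, and separate dose lines would rescue some subjects.
- That baseline steroid use disappears. Tables 14.1.6 and 14.1.8 still show it, in broad categories and not by ATC class and preferred term.

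**Conclusion.** The concern holds in a narrow form: the definition in SAP 11.6 is wrong as written, and the severity is minor. One of seven date patterns is unassigned and one more depends on how ongoing is read. The unassigned pattern is one that the protocol anticipates, with tapers from 5 to 20 mg/day ending at about Day 28 to 56.

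Applied literally, the rule makes Table 14.3.6.2 and Listing 16.4.11 under-report on-study medication. The effect is descriptive; no efficacy or safety test changes. The number of subjects affected cannot be determined, because the documents give neither the number on steroids, nor how many will be tapered to zero, nor how dose steps are entered in the eCRF.

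The conclusion rests on the literal text of the definition and on complete stop dates. The taper days further assume weekly 5 mg cuts beginning in Week 4.

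**What to change.** In SAP 11.6, define concomitant as any medication taken on or after the date of first dose, regardless of start date. State that this includes medications ongoing or stopped on study, and those whose stop date cannot be shown to precede first dose. Keep prior as stopped before first dose. Every record then falls in exactly one class, and the existing tables and listings follow without redesign.

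The cost is one SAP sentence and the matching program flag. No new data, protocol amendment or change to any test is needed. The drawback is a longer Table 14.3.6.2, because background drugs taken on study will appear in it. That table will still count use per drug only and will not show the timing of a taper.

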12 VALIDATION

All tables, figures and listings will be subject to independent quality control and visual review. Unique tables will be independently programmed. Findings will be documented in a quality control form and actions taken will also be documented.

The completed form will be reviewed and signed by both programmers and by the head of biostatistics.

14 LIST OF TABLES, FIGURES AND LISTINGS

14.1 LIST OF TABLES

Demo	graphic	: Data
	zi apiii	_ i ∠aia

[figure not shown]
Demographic Data		All C H. J
Table 14.1.1	Screening Failures	All Enrolled Patients
Table 14.1.2	Study Termination and Primary Reason for Withdrawal	All Randomised Patients
Table 14.1.3	Patient Disposition	All Randomised Patients
Table 14.1.4	Demographics and Baseline Characteristics	Full Analysis Set
Table 14.1.5.1	Medical History	Full Analysis Set
Table 14.1.5.2	Current Medical Conditions	Full Analysis Set
Table 14.1.6	Disease History	Full Analysis Set
Table 14.1.7	Baseline Faecal Calprotectin Levels, Total Mayo Score, Partial Mayo Score and SF-36 Component Summary Measures Scores	Full Analysis Set
Table 14.1.8	Baseline Medication for UC and Prior Biological Failure	Full Analysis Set
Efficacy Data		
Table 14.2.1.1	Analysis of Patients Achieving Clinical Remission	PP Set
Table 14.2.1.2	Analysis of Patients Achieving Clinical Remission	Full Analysis Se
Table 14.2.2.1	Analysis of Faecal Calprotectin Levels	PP Set
Table 14.2.2.2	Summary of Total Mayo Score	PP Set
Table 14.2.2.3	Summary of Partial Mayo Score	PP Set
Table 14.2.2.4	Summary of Patients Achieving Endoscopic Remission and Mucosal Healing	PP Set
Table 14.2.2.5	Summary of Patients Achieving Clinical Response	PP Set
Table 14.2.2.6	Summary of SF-36 Component Summary Measures Scores	PP Set

Safety Data

Safety Data		
Table 14.3.1.1	Summary of Adverse Events	Safety Set
Table 14.3.1.2.1	Summary of Treatment-Emergent Adverse Events: Period I	Safety Set
Table 14.3.1.2.2	Summary of Treatment-Emergent Adverse Events: Period 2	Safety Set
Table 14.3.1.3.1.1	Treatment-Emergent Adverse Events, by SOC and PT: Period I	Safety Set
Table 14.3.1.3.1.2	Treatment-Emergent Adverse Events, by SOC and PT: Period 2	Safety Set
Table 14.3.1.3.2.1	Severe Treatment-Emergent Adverse Events, by SOC and PT: Period I	Safety Set
Table 14.3.1.3.2.2	Severe Treatment-Emergent Adverse Events, by SOC and PT: Period 2	Safety Set
Table 14.3.1.3.3.1	Serious Treatment-Emergent Adverse Events, by SOC and PT: Period I	Safety Set
Table 14.3.1.3.3.2	Serious Treatment-Emergent Adverse Events, by SOC and PT: Period 2	Safety Set
Table 14.3.1.3.4.1	Drug-Related Treatment-Emergent Adverse Events, by SOC and PT: Period 1	Safety Set
Table 14.3.1.3.4.2	Drug-Related Treatment-Emergent Adverse Events, by SOC and PT: Period 2	Safety Set
Table 14.3.1.3.5.1	Serious Drug-Related Treatment-Emergent Adverse Events, by SOC and PT: Period I	Safety Set
Table 14.3.1.3.5.2	Serious Drug-Related Treatment-Emergent Adverse Events, by SOC and PT: Period 2	Safety Set
Table 14.3.1.3.6.1	Treatment-Emergent Adverse Events Leading to Study Drug Discontinuation, by SOC and PT: Period I	Safety Set
Table 14.3.1.3.6.2	Treatment-Emergent Adverse Events Leading to Study Drug Discontinuation, by SOC and PT: Period 2	Safety Set
Table 14.3.1.3.7.1	Treatment-Emergent Adverse Events, by Intensity and SOC and PT: Period I	Safety Set
Table 14.3.1.3.7.2	Treatment-Emergent Adverse Events, by Intensity and SOC and PT: Period 2	Safety Set
Table 14.3.2.1.1	Summary of Haematology Parameters	Safety Set
Table 14.3.2.1.2	Summary of Biochemistry Parameters	Safety Set
Table 14.3.2.1.3	Summary of Stool Results	Safety Set
Table 14.3.2.2.1	Shift Table of Haematology Parameters	Safety Set

GROUP

Table 14.3.2.2.2	Shift Table of Biochemistry Parameters	Safety Set
Table 14.3.2.2.3	Shift Table of Urinalysis Parameters	Safety Set
Table 14.3.3	Vital Signs, including Weight	Safety Set
Table 14.3.4.1	12-lead Electrocardiogram	Safety Set
Table 14.3.4.2	Shift Table of 12-lead Electrocardiogram	Safety Set
Table 14.3.5	Study Drug Exposure	Full Analysis Set
Table 14.3.6.1	Prior Medications	Full Analysis Set
Table 14.3.6.2	Concomitant Medications	Full Analysis Set

[figure not shown]
14.2 LIST OF LISTINGS

Patient Data Listings

Listing 16.2.1	Discontinued Patients
Listing 16.2.2	Protocol Deviations
Listing 16.2.3	Analysis Datasets
Listing 16.2.4	Demographic Data
Listing 16.2.5	Study Drug Exposure and Compliance
Listing 16.2.6	Efficacy Response Data
Listing 16.2.7	Adverse Event Listing
Listing 16.2.8.1	Laboratory Measurements: Haematology
Listing 16.2.8.2	Laboratory Measurements: Biochemistry
Listing 16.2.8.3	Laboratory Measurements: Stool Results

Individual Patient Data Listings (Archive)

Listing 16.4.1	Final Status
Listing 16.4.2	Patient Visit Dates
Listing 16.4.3.1	Inclusion Criteria
Listing 16.4.3.2	Exclusion Criteria
Listing 16.4.4	Medical History
Listing 16.4.5.1	Raw Efficacy Scores: Mayo Score
Listing 16.4.5.2.1	Raw Efficacy Scores: SF-36 Questionnaire
Listing 16.4.5.2.2	Raw Efficacy Scores: SF-36 Component Summary Measures and Domain Scales

GROUP

Listing 16.4.6	Study Drug Administration
Listing 16.4.7	Vital Signs
Listing 16.4.8	Physical Examination
Listing 16.4.9	12 Lead ECG
Listing 16.4.10	Prior Medications
Listing 16.4.11	Concomitant Medications
Listing 16.4.12	Procedures/Non-Drug Therapies
Listing 16.4.13	Urine Pregnancy Test
Listing 16.4.14	Laboratory Samples Collection

